#### **Plan for Review of Pauses and Resuming Rules:**

Study product administration and enrollments would resume only if review of the AEs that caused the pause results in a recommendation to permit further study product administrations and study enrollments. The reviews to make this decision will occur as follows:

- **Pauses for related SAEs:** The IND Sponsor, with participation by the PI, will conduct the review and make the decision to resume, amend or close the study and will notify the FDA and IRB accordingly.
- **Pauses for Grade 3 or higher related AEs:** The IND Sponsor MO, in consultation with the PI, will conduct the review and make the decision to resume, amend or close the study for the Grade 3 or higher AEs that meet criteria for pausing the study. As part of the pause review, the reviewers will also advise on whether the study needs to be paused again for any subsequent events of the same type. The FDA and the IRB will be notified of Grade 3 or higher pause reviews and of the IND Sponsor's decisions.

## 5. SAFETY AND ADVERSE EVENT REPORTING

### 5.1 Adverse Events

An AE is any untoward or unfavorable medical occurrence in a human subject, including any abnormal sign (e.g., abnormal physical exam or laboratory finding), symptom, or disease temporally associated with the use of study treatment, whether considered related to the study treatment.

AEs will be graded according to the *DAIDS Table for Grading the Severity of Adult and Pediatric Adverse Events* (see Appendix IV).

Reporting of all AEs will occur during the period from study product administration at Day 0 through 28 days after study product administration. From Day 28 through completion of study participation, only SAEs and new chronic medical conditions that require ongoing medical management will be recorded as AEs in the study database.

### 5.2 Serious Adverse Events

An SAE is defined in 21 CFR 312.32 as follows: “An adverse event or suspected adverse reaction is considered serious if, in the view of either the investigator or the sponsor, it results in any of the following outcomes: Death, a life-threatening adverse event, inpatient hospitalization or prolongation of existing hospitalization, a persistent or significant incapacity or substantial disruption of the ability to conduct normal life functions, or a congenital anomaly/birth defect. Important medical events that may not result in death, be life-threatening, or require hospitalization may be considered serious when, based upon appropriate medical judgment, they may jeopardize the patient or subject and may require medical or surgical intervention to prevent one of the outcomes listed in this definition. Examples of such medical events include allergic bronchospasm requiring intensive treatment in an emergency room or at home, blood dyscrasias or convulsions that do not result in inpatient hospitalization, or the development of drug dependency or drug abuse.”

“Life-threatening” refers to an AE that at occurrence represents an immediate risk of death to a subject. An event that may cause death if it occurs in a more severe form is not considered life-threatening. Similarly, a hospital admission for an elective procedure is not considered a SAE.

### 5.3 Adverse Event Reporting to the IND Sponsor

AEs that meet SAE Reporting Requirements must be reported and submitted by the clinical site on an expedited basis to the IND Sponsor, VRC/NIAID/NIH, according to Sponsor guidelines as follows:

- results in death
- is life threatening
- results in persistent or significant disability/incapacity
- requires unplanned inpatient hospitalization or prolongation of existing hospitalization
- is a congenital anomaly/birth defect in the offspring of a study subject
- is an important medical event that may jeopardize the subject or may require intervention to prevent one of the other outcomes listed above.

In addition, any event, regardless of severity, which in the judgment of an investigator represents a SAE, may be reported on an expedited basis.

An investigator will communicate an initial SAE report within 24 hours of site awareness of occurrence to the IND sponsor by email to the VRC Protocol Operations Office (see Appendix II).

A written report by the investigator should be submitted to the IND Sponsor within 3 working days. In order for the IND Sponsor to comply with regulations mandating sponsor notification of specified SAEs to the FDA within 7 and/or 15 calendar days, the investigator must submit additional information as soon as it is available.

### 5.3.1 IND Sponsor Reporting to the FDA

It is the responsibility of the IND Sponsor to make the determination of which SAEs are “serious and unexpected suspected adverse reactions” (SUSARs) as defined in 21 CFR 312.32.

- *Suspected adverse reaction* means any AE for which there is a reasonable possibility that the drug caused the AE.
- *Unexpected adverse event* means an AE that is not listed in the IB or is not listed at the specificity or severity that has been observed.

All SUSARs, as determined by the IND Sponsor, will be reported to the FDA as IND Safety Reports and IND Safety Reports will be provided to the IRB.

The IND Sponsor will also submit an IND Annual Report of the progress of the investigation to the FDA as defined in 21 CFR 312.33.

## 5.4 Reporting to the Institutional Review Board

### 5.4.1 Unanticipated Problem (UP) Definition

An Unanticipated Problem (UP) is defined as any incident, experience, or outcome that meets all three of the following criteria:

- unexpected in nature, severity, or frequency in relation to the research risks that are described in the protocol, informed consent, IB, other study documents or in consideration of the characteristics of the subject population being studied; **and**
- related to participation in the research; **and**
- suggests that the research places subjects or others at a greater risk of harm (including physical, psychological, economic, or social harm) than was previously known or recognized.

**Serious UP:** An UP that meets the definition of a SAE or compromises the safety, welfare or rights of subjects or others.

An UP that is not an Adverse Event (UPnonAE) is an unanticipated problem that does not fit the definition of an AE, but which may, in the opinion of the investigator, involve risk to the subject, affect others in the research study, or significantly impact the integrity of research data. Such events would be considered a non-serious UP. For example, we will report occurrences of breaches of confidentiality, accidental destruction of study records or samples, or unaccounted-for study drug.

### 5.4.2 Protocol Deviation Definition

A Protocol Deviation is defined as any change, divergence, or departure from the IRB-approved study procedures in a research protocol. Protocol deviations are designated as serious or non-serious and further characterized as follows:

- Those that occur because a member of the research team deviates from the protocol.
- Those that are identified before they occur but cannot be prevented.
- Those that are discovered after they occur.

Serious Protocol Deviation: A deviation that meets the definition of a SAE or compromises the safety, integrity of the data, welfare or rights of subjects or others.

### 5.4.3 Non-Compliance Definition

Non-compliance is the failure to comply with applicable NIH Human Research Protections Program (HRPP) policies, IRB requirements, or regulatory requirements for the protection of human subjects. Non-compliance is further characterized as serious, continuing or minor.

“Serious non-compliance” is defined as non-compliance that:

- Increases risks, or causes harm, to subjects
- Decreases potential benefits to subjects
- Compromises the integrity of the NIH-HRPP
- Invalidates the study data

“Continuing non-compliance” is non-compliance that is recurring.

“Minor non-compliance” is non-compliance that is neither serious nor continuing.

### 5.4.4 Expedited Reporting to the IRB

The following will be reported to the NIAID IRB within 7 calendar days of investigator awareness:

- Serious and non-serious UP
- Deaths
- Serious protocol deviations
- Serious or continuing non-compliance
- SAEs that are possibly, probably, or definitely related to the research regardless of expectedness

The following waiver applies to reporting anticipated protocol deviations and expected UPnonAEs: Anticipated deviations in the conduct of the protocol will not be reported to the IRB unless they occur at a rate greater than anticipated by the study team. Expected AEs will not be reported to the IRB unless they occur at a rate greater than that known to occur in healthy adults. If the rate of these events exceeds the rate expected by the study team, the events will be classified and reported as though they are unanticipated problems.

### 5.4.5 Annual Reporting to the IRB

The following will be reported to the NIAID IRB in summary at the time of Continuing Review:

- Serious and non-serious UPs
- Expected SAEs that are possibly, probably, or definitely related to the research
- SAEs that are not related to the research
- All AEs, except expected AEs granted a waiver of reporting
- Serious and non-serious Protocol Deviations
- Serious, continuing, and minor non-compliance
- Any trends or events which in the opinion of the investigator should be reported

## 6. STATISTICAL CONSIDERATIONS

### 6.1 Overview

This is a Phase I, open-label, dose-escalation study of the safety and pharmacokinetics of a human monoclonal antibody, MAb114, administered intravenously to healthy adults.

### 6.2 Objectives

The primary objectives of the study are to evaluate the safety and tolerability of MAb114, to evaluate the pharmacokinetics of MAb114, and to estimate the half-life of MAb114 in serum.

### 6.3 Size and Accrual

#### 6.3.1 Sample Size Considerations

This study is primarily descriptive. For safety analysis, the goal is to identify safety concerns associated with different MAb114 dosages. There may be as few as 3 to 10 subjects in a group; therefore, this section considers group sizes of  $n=3$ , 5 and 10.

The ability to identify serious adverse experiences is best expressed by the maximum true rate of SAE that would unlikely be observed and the minimum true SAE rate that would very likely be observed. Within a group of size  $n=3$ , there is an 80% chance of observing at least 1 event if the true rate is no less than 0.42 and a 90% chance of observing no event if the true rate is no bigger than 0.035. Within a group of size  $n=10$ , there is at least an 80% chance of observing at least 1 event if the true rate is no less than 0.15 and at least a 90% chance of observing no event if the true rate is no bigger than 0.1.

Probabilities of observing 0 or more than 1 event are presented in **Table 4** for a range of possible true event rates. These calculations provide a complete picture of the sensitivity of this study design to identify potential safety problems with the study agent. For example, within the group of size  $n=3$ , if the true event rate is 0.1, then there is a 73% probability of observing no event and a 2.8% probability of observing more than 1 event; while, within the group of size  $n=10$ , if the true event rate is 0.1, then there is a 35% probability of observing no event and an 26% probability of observing more than 1 event.

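### For n=10 the plan claims at least a 90% chance of no event at true rates up to 0.1; at 0.1 the chance is 35%, and the threshold should be about 0.01.

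*Combined protocol and SAP*

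**What the plan says.** Section 6.3.1 considers group sizes of 3, 5 and 10. It presents two quantities as the best summary of the ability to identify serious adverse events: "the maximum true rate of SAE that would unlikely be observed and the minimum true SAE rate that would very likely be observed".

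For n=3 it puts the upper threshold at 0.42 (an 80% chance of one or more events) and the lower one at 0.035 (a 90% chance of none). For n=10 the upper threshold is 0.15, again for an 80% chance of one or more events. The lower threshold for n=10 is worded as follows: "at least a 90% chance of observing no event if the true rate is no bigger than 0.1". No thresholds are given for n=5.

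The next paragraph says that for a group of 10, "if the true event rate is 0.1, then there is a 35% probability of observing no event". Table 4, in the n=10 columns at a true rate of 0.1, shows 0.349 for no event and 0.264 for more than one. Table 3 assigns 10 subjects to Group 3, the 50 mg/kg group.

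**The concern.** Two statements in one section give different probabilities for the same group size and event rate: at least 90% in one paragraph, 35% in the next. Both cannot be right.

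The ordering of the thresholds is also impossible. The rate at which a group is 90% likely to show no event must fall as the group grows, yet the plan gives 0.035 for 3 subjects and 0.1 for 10.

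Safety is the primary objective, and the section puts these thresholds forward as the headline description of what the study can reveal. A reader who relied on the sentence would believe that an event with a 10% true rate has at most a 10% chance of appearing among the 10 subjects at the highest dose. That reader could take a single event as a sign of a rate above 10%, and could treat zero events as almost uninformative about a 10% rate.

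**Working it through.** **Inputs.** Group sizes 3 and 10, and the four stated thresholds, from section 6.3.1; the n=10 entries from Table 4.

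**Formulas.** With n independent subjects and true rate p:

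- Pr(no event) = (1 − p)^n
- Pr(at least one event) = 1 − (1 − p)^n
- rate giving a 90% chance of no event: p = 1 − 0.9^(1/n)
- rate giving an 80% chance of at least one event: p = 1 − 0.2^(1/n)

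**Step 1: the four stated thresholds.**

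| n | Statement | Stated rate | Probability at that rate | Exact threshold | Reproduces? |
|---|---|---|---|---|---|
| 3 | 80% chance of at least one event | 0.42 | 1 − 0.58^3 = 0.805 | 1 − 0.2^(1/3) = 0.415 | yes |
| 3 | 90% chance of none | 0.035 | 0.965^3 = 0.899 | 1 − 0.9^(1/3) = 0.0345 | yes, to rounding |
| 10 | at least 80% chance of at least one event | 0.15 | 1 − 0.85^10 = 0.803 | 1 − 0.2^(1/10) = 0.149 | yes |
| 10 | at least 90% chance of none | 0.1 | 0.9^10 = 0.349 | 1 − 0.9^(1/10) = 0.0105 | **no** |

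**Step 2: size of the error.** At a rate of 0.1 the probability of no event is 0.349 against a claimed minimum of 0.90, a gap of 55 percentage points. The probability of at least one event is 1 − 0.349 = 0.651, against an implied maximum of 0.10. The stated rate is 0.1 / 0.01048 = 9.5 times the correct one.

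**Step 3: rates below 0.1.** The statement covers all rates up to 0.1, and 35% is the value at the top of that range. At 0.05 the probability of no event is 0.95^10 = 0.599 (also in Table 4), still far short of 90%. At 0.01 it is 0.99^10 = 0.904. The claim is therefore true only up to about 0.0105.

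**Step 4: other readings.** At n=10 and p=0.1, the probability of at most one event is 0.736 and of at most two events 0.930. Neither means no event, and neither equals 0.90. With a rate of 0.1, a 90% chance of no event occurs only for n=1, since 0.9^1 = 0.9.

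**The case against.** The strongest reply concerns weight, since the arithmetic cannot be defended.

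- The study is described as primarily descriptive, and no group size is derived from this figure.
- Dose escalation (section 4.3) rests on review of Day 7 safety data. Pausing (section 4.5) rests on counts of related events. The safety analysis (section 6.4.3) uses exact 95% confidence intervals.
- Group 3 is the last dose level, so no escalation decision follows it.
- The right probability stands in the next paragraph and in Table 4.
- The error understates what 10 subjects can reveal. The threshold that supports a claim of detection, 80% at a rate of 0.15, is correct.

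All of this stands. It also limits the likely harm: for one event in 10, Table 5 gives an interval of 0.002 to 0.445, which plainly includes rates well below 10%. Anyone using the planned interval would not conclude that the rate exceeds 10%, so misreading is a possibility for someone who relies on the sentence alone.

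None of it makes the sentence true. The section itself names these thresholds as its main summary, and one of the two is wrong for the largest group. A correct value elsewhere leaves the reader to decide which statement to believe.

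**Conclusion.** The concern holds. The n=10 statement about observing no event is false as written: the probability at a true rate of 0.1 is 35%, and 90% is reached only at about 0.0105. The error is confined to the lower threshold, the highest rate at which events would probably go unseen; the upper threshold of 0.15 is right.

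The conclusion rests only on the binomial model with independent subjects and a common event rate, which is the model that reproduces the plan's other three thresholds and the n=10 entries of Table 4 used here. The pattern fits a misplaced decimal, 0.1 for 0.01, but that cause is an inference. The correction is needed because the sentence misstates a headline safety operating characteristic, although it changes no decision rule, sample size or analysis.

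**What to change.** In the n=10 sentence of section 6.3.1, change the rate in the 90% no-event statement from 0.1 to 0.01. The wording of at least 90% then holds, since 0.99^10 = 0.904. Rounding to 0.0105 would fall just short (0.8998), so 0.01 is the better figure to print.

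Optionally, add the n=5 thresholds, since the section says it considers that size and gives none: at least an 80% chance of one or more events at a rate of 0.28 or higher (exact 1 − 0.2^(1/5) = 0.275), and at least a 90% chance of none at 0.02 or lower (exact 1 − 0.9^(1/5) = 0.0209). This helps completeness and is not needed to correct the error.

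The cost is one figure in the text, with no change to design, enrollment or analysis. In the same edit, check Table 5: the lower limit for 2/3 is printed as 0.94, above the observed rate of 0.667. By symmetry with the upper limit for 1/3, it should be 1 − 0.906 = 0.094.

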**Table 4: Probability of Event for Different Scenarios**

True event rate	Within a group (n=3)		Within a group (n=5)		Within a group (n=10)	
	Pr (0 event observed)	Pr (more than 1 event observed)	Pr (0 event observed)	Pr (more than 1 event observed)	Pr (0 event observed)	Pr (more than 1 event observed)
0.05	0.857	0.007	0.774	0.023	0.599	0.086
0.1	0.729	0.028	0.590	0.081	0.349	0.264
0.2	0.512	0.104	0.328	0.263	0.107	0.624
0.3	0.343	0.216	0.168	0.472	0.028	0.851
0.4	0.216	0.352	0.078	0.663	0.006	0.954

**Table 5** gives the upper and lower bounds for 95% exact binomial confidence intervals (CIs) for all possible number of observed events within a group. Within the group of size n=3, if no subjects experience the event, the 95% exact 2-sided CI for the true rate has an upper bound of 0.708; if all subjects experience the event, the 95% exact 2-sided CI for the true rate has a lower bound of 0.292. Within the group of size n=5, if no subjects experience the event, the 95% exact 2-sided CI for the true rate has upper bound of 0.522; if all subjects experience the event, the 95% exact 2-sided CI for the true rate has a lower bound of 0.478. Within the group of size n=10, if no subjects experience the event, the 95% exact 2-sided CI for the true rate has upper bound of 0.308; if all subjects experience the event, the 95% exact 2-sided CI for the true rate has a lower bound of 0.692.

**6.4 Statistical Analysis**

**6.4.1 Analysis Variables**

The analysis variables consist of baseline, pharmacokinetic, and safety variables for the primary and secondary objective analyses.

**6.4.2 Baseline Demographics**

Baseline characteristics including demographics and laboratory measurements will be summarized using descriptive statistics.

**6.4.3 Safety Analysis**

Summaries of the number and percentage of subjects experiencing any AE or reactogenicity will be tallied by group and presented along with exact 95% confidence intervals for the proportion.

Solicited Adverse Events:

Solicited AE data is collected after each dose administered in this study. The number and percentage of subjects experiencing each type of solicited sign or symptom will be tabulated by severity. For a given sign or symptom, each subject’s solicited AEs will be counted once under the maximum severity for all assessments.

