**4.1.1 Inclusion Criteria**

*A volunteer must meet all of the following criteria:*

1. Able and willing to complete the informed consent process.
2. Available for clinical follow-up through the last study visit.
3. 18 to 60 years of age.
4. In good general health without clinically significant medical history.
5. Willing to have blood samples collected, stored indefinitely, and used for research purposes.
6. Able to provide proof of identity to the satisfaction of the study clinician completing the enrollment process.
7. Physical examination without clinically significant findings within the 84 days prior to enrollment.
8. Have screening laboratory values within 84 days prior to enrollment that meet the following criteria:
  - WBC 2,500-12,000/mm^3

- WBC differential either within institutional normal range or accompanied by the Principal Investigator (PI) or designee approval
- Platelets = 125,000 – 400,000/mm^3
- Hemoglobin within institutional normal range or accompanied by the PI or designee approval
- Creatinine  $\leq 1.1$  x upper limit of normal (ULN)
- ALT  $\leq 1.25$  x ULN
- Negative for human immunodeficiency virus (HIV) infection by a Food and Drug Administration (FDA) approved method of detection
- Negative for Hepatitis B core antibody (HBcAb) and Hepatitis C virus antibody (HCV Ab)

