#### **4.2.4 Solicited Adverse Events and Clinical Follow-up**

Subjects will be asked to record temperature and systemic symptoms daily for 3 days after the study product administration. Subjects will be trained and encouraged to use the electronic database to record reactogenicity but will have the option to use a paper diary card. When the 3-day diary parameters are recorded directly by the subject into the database, the subject's electronic record will be available to clinicians in real time and will be the source for these data. If concerns arise based on the subject's report of symptoms, clinicians may follow up with additional phone calls during the reactogenicity period as needed. The paper diary will be the source document, if used by the subject. When neither a paper nor electronic diary is available from the subject, the clinician will note the source of reactogenicity information recorded in the study database.

For this study, solicited systemic parameters occurring during the 3 days after receipt of study product will include: unusually tired/feeling unwell, muscles aches, headache, chills, nausea and joint pain. Subjects will also record highest measured temperature daily. Subject diaries are reviewed for accuracy and completeness at follow-up visits and reactogenicity is recorded without an attribution assessment. Clinicians will follow and collect resolution information for any reactogenicity symptoms that are not resolved within 3 days.

Local symptoms will be assessed and recorded by the clinicians. Local reactogenicity parameters will include pain/tenderness, swelling, redness, bruising, and pruritus (itchiness) at the product administration site. Clinicians will assess the study product administration site(s) for local reactogenicity on the day of product administration after completion of the administration and during the scheduled follow-up time points as noted in the Schedule of Evaluations (Appendix III).

Events that may require a clinic visit include rash, urticaria, fever of 38.6°C (Grade 2) or higher lasting greater than 24 hours or significant impairment in the activities of daily living (such as those consistent with Grade 2 or higher impairment). Additionally, arthralgia or other clinical concerns may prompt a study visit based on the judgment of a study clinician.

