**Footnotes:**

 Day 0=day of product administration. Day 0 is preferably scheduled within 14 days after enrollment at Visit 01R, but may be scheduled up to 28 days after enrollment.

 Screening: All screening evaluations including laboratory tests, medical history and complete physical exam must be completed within 84 days of enrollment.

 Physical exam: Screening includes complete physical exam with vital signs, height and weight. Day 0 physical exam includes vital signs (blood pressure, temperature and pulse) and weight (used for ordering the study product which is based on a “mg/kg” dose). At other visits if medically indicated, a targeted exam is performed. Otherwise only blood pressure, pulse and temperature are required.

 Medical history: Screening, 01R and Day 0 evaluations include a complete medical history to evaluate eligibility criteria as defined in Section 4.1. At other visits, an interim medical history will be completed.

 Concomitant medications: Concomitant medications must be entered in the database at enrollment and updated as required in Section 4.2.7.

 Study product administration: Group 1 subjects will receive a single infusion of 5 mg/kg IV, Group 2 subjects will receive a single infusion of 25 mg/kg IV, and Group 3 subjects will receive a single infusion of 50 mg/kg IV.

 Administration Site Evaluation: Clinicians will assess the product administration site on Days 1, 2 and 7 and record any findings in the database. Any signs or symptoms unresolved by Day 7 should continue to be evaluated until resolved.

 Reactogenicity Diary: Subjects will begin to record 3-day systemic reactogenicity after study product administration as noted in Section 4.2.4. Clinicians will review with the subject at a minimum on Days 1, 2 and 7. If any reported reactogenicity is unresolved by Day 3, it will continue to be reviewed with the subject until resolved which may require an interim phone contact. Data from the diary will be recorded in the database as noted in Section 4.2.4.

 Pregnancy test and pregnancy prevention counseling are required at visits as indicated for women of reproductive potential. Negative pregnancy test results must be confirmed for women of reproductive potential prior to MAb114 administration.

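### No pre-infusion score is specified for the six solicited systemic symptoms, so a symptom already present on Day 0 can be tabulated as reactogenicity

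*Combined protocol and SAP*

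**What the plan says.** **Collection.** Section 4.2.4 solicits six systemic symptoms, "unusually tired/feeling unwell, muscles aches, headache, chills, nausea and joint pain", plus the highest daily temperature, for 3 days after dosing. Appendix III (first schedule, footnote 8) gives the starting point: "Subjects will begin to record 3-day systemic reactogenicity after study product administration". Section 4.2.4 adds that "reactogenicity is recorded without an attribution assessment".

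**Baseline.** Sections 4.2.2 and 4.2.3 and Appendix III (visit windows and footnotes 3 and 4) require temperature, blood pressure, pulse, a targeted examination and a complete medical history on Day 0. They make the pre-infusion Day 0 evaluations the baseline for later safety and AE assessment. None of these passages asks for the six symptoms to be graded before infusion.

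**Eligibility.** The nearest inclusion criterion in 4.1.1 is general: "In good general health without clinically significant medical history".

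**Analysis.** Section 6.4.3 tallies subjects with any AE or reactogenicity by group, "presented along with exact 95% confidence intervals for the proportion". For each solicited symptom it tabulates subjects by severity, and each subject's "solicited AEs will be counted once under the maximum severity for all assessments". Section 6.4.4 makes these 3-day solicited events the main content of the tolerability evaluation, which is part of the primary objectives in 3.1.

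**The concern.** All six systemic symptoms are non-specific and can be present in a healthy adult on any day. If a subject arrives with one and reports it in the diary that evening, the plan as written counts it at its highest post-dose grade, exactly like a symptom that began after infusion.

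The other safety data have some protection. Section 6.4.3 displays laboratory values at baseline as well as during the study, and it tabulates unsolicited AEs by relationship to treatment. Solicited systemic events have neither a stated comparison with Day 0 nor an attribution, and there is no control arm to show the background rate.

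What is at stake is the accuracy of a primary descriptive summary in very small groups. Section 6.3.1 says "There may be as few as 3 to 10 subjects in a group". Section 6.4.4 also intends this summary to guide which parameters are solicited in larger studies.

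**Working it through.** **1. The plan's own interval.** The 6.3.1 text puts the following limit at 0.708: "Within the group of size n=3, if no subjects experience the event, the 95% exact 2-sided CI for the true rate has an upper bound". Check: when none of n subjects has the event, the exact (Clopper-Pearson) upper limit is 1 − 0.025^(1/n). With n = 3 this is 1 − 0.2924 = 0.7076, which agrees.

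**2. One subject with a pre-existing symptom.** Suppose that nobody in the group has a drug-related solicited event and one subject carries a symptom across infusion.
- For 1 of 3, the lower bound is 1 − 0.975^(1/3) = 0.0084.
- The upper bound p solves (1 − p)³ + 3p(1 − p)² = 0.025, which gives 0.9057.
- Both agree with the 1/3 row of Table 5.

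| Group | Without the subject | With the subject | Shift in point estimate |
|---|---|---|---|
| 1 (n = 3) | 0/3: 0 to 0.708 | 1/3: 0.008 to 0.906 | 33 points |
| 2 (n = 5) | 0/5: 0 to 0.522 | 1/5: 0.005 to 0.716 | 20 points |
| 3 (n = 10) | 0/10: 0 to 0.308 | 1/10: 0.002 to 0.445 | 10 points |

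The intervals are as printed in Table 5.

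**3. How often.** The documents give no background rate. Let q be the probability that a dosed subject carries at least one of the six symptoms from before infusion into the diary. This q is an assumption, shown over a range. The chance of at least one such subject is 1 − (1 − q)^n. For example, with q = 5% and n = 3 it is 1 − 0.95³ = 14.3%.

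| Assumed q | n = 3 | n = 5 | n = 10 | n = 18 |
|---|---|---|---|---|
| 1% | 3.0% | 4.9% | 9.6% | 16.6% |
| 2% | 5.9% | 9.6% | 18.3% | 30.5% |
| 5% | 14.3% | 22.6% | 40.1% | 60.3% |
| 10% | 27.1% | 41.0% | 65.1% | 85.0% |
| 20% | 48.8% | 67.2% | 89.3% | 98.2% |

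**4. Direction and size of the bias.** If r is the rate of solicited events that truly begin after infusion, and the two are independent, the tabulated rate is 1 − (1 − q)(1 − r). The excess over r is q(1 − r), which is never negative. With r = 10%, the tabulated rate is 11.8%, 14.5% or 19.0% for q = 2%, 5% or 10%.

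**5. The data reported so far.** Section 1.6.1 reports three subjects with mild systemic symptoms. It prints 3 of 11, but the 23.1% beside it is 3/13. If one of the three had been symptomatic before infusion, the rate of new events would be 2/13 = 15.4%. Nothing suggests that this happened. The point is that no pre-dose score is specified that would settle it.

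**6. Who can still be scored.** Section 1.6.1 gives 3 + 5 + 5 = 13 subjects dosed as of 24 July 2018. The minimum of 18 leaves 18 − 13 = 5, and the maximum of 30 leaves 30 − 13 = 17.

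**The case against.** **The baseline exists.** A reader might infer that there is no pre-infusion baseline at all. The documents do not support that. Temperature, itself a solicited parameter, is measured before infusion. A complete history is taken on Day 0 to evaluate eligibility, a targeted examination is done, and the protocol declares these the baseline. An obviously ill volunteer could be identified under the general criteria. This stands. It narrows the gap to two things: no score for the six symptoms, and no rule in 6.4.3 for using what Day 0 provides.

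**The table does not assign cause.** Because solicited events carry no attribution, the table reports what was recorded after dosing and does not claim a drug effect. That is correct, and the analysis is descriptive. But the table is headed as solicited AEs and feeds the tolerability conclusion, and no second count is planned to separate old from new.

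**Escalation is not driven by these rates.** A reader might infer that a chance symptom could alter dose escalation or pause the study. Section 4.3 rests escalation on the safety review team's judgement, with no numerical threshold. Section 4.5 requires related events and exempts self-limited Grade 3 solicited reactogenicity. This objection stands in full. An upward bias is also the cautious direction for safety.

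**It is late.** Groups 1 and 2 and half of Group 3 had already been dosed. A pre-dose score cannot be obtained for them afterwards, and Group 3 would hold two kinds of data. This limits the benefit of the change but does not remove it.

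**The frequencies are assumed.** They are, and they presume that the symptom passes the Day 0 checks and persists into the diary. They show a range and are not an estimate.

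**Conclusion.** The point holds in a limited form. A solicited systemic symptom present before infusion can be counted as reactogenicity, because no pre-dose score is specified and 6.4.3 does not refer to Day 0. The effect is an upward bias in an uncontrolled summary. One such subject changes the point estimate by 33, 20 or 10 percentage points in Groups 1, 2 and 3, provided that subject has no other solicited event. The probability of at least one such subject in Group 1 runs from 3.0% to 48.8% over an assumed q of 1% to 20%. The documents cannot narrow that range.

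It would go too far to say that intercurrent illness is being counted as a drug effect. The documents show only that it can be, and there is no evidence that it has been. A Day 0 score would also not separate an illness that begins after infusion.

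The change is worth making because it is cheap and bears on a primary objective. It does not threaten the escalation decisions.

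**What to change.** 1. **Subjects still to be dosed:** record the six systemic symptoms once before infusion on Day 0, using the existing diary items and grades, beside the temperature already taken.
2. **Section 6.4.3:** keep the all-events count and add a count of solicited events that are new or worsened relative to Day 0. State the denominator as subjects with a pre-dose score. For temperature, a Day 0 value is required of every subject, so the new-or-worsened count can cover all of them.
3. **Subjects already dosed:** list any solicited symptom documented in the Day 0 history or examination, and any raised Day 0 temperature, next to that subject's solicited events.

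**Cost:** one extra diary entry per subject, one extra table column and one listing. The new-or-worsened symptom count would rest on at least 5 of the minimum 18 subjects. If enrollment stops at 18 in the planned group sizes, those 5 are all in Group 3, so the column would not support a comparison between doses.

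Whether to add a Day 0 criterion for acute illness is a clinical decision for the sponsor and is not part of this change.
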